3.3 STUDY OUCOME MEASURES

3.3.1 **Primary endpoints**

All-cause mortality at day 30 following randomization (i.e. 30 day mortality)

3.3.2 **Secondary endpoints:**

[figure not shown]
- All-cause mortality at 48 hours and day 7, 60, 180
- VA-ECMO duration
- Composite endpoint of death, cardiac transplant, escalation to LVAD, stroke at days 30, 60, 180
- Cumulated amount of administered fluids and duration of vasopressors use in ICU
- Duration to normalization of lactate
- Number of days alive without organ failure(s), defined with the SOFA score and its components (respiratory, liver, coagulation and renal), between inclusion, D7 and D30
- Duration of mechanical ventilation and the number of days between inclusion and day 30/ day 60/ day 180, alive without mechanical ventilation
- Number of days alive without renal replacement therapy, and the number of days, between inclusion and day 30, day 60 and day 180, without renal replacement therapy

- Duration of ICU stay, of hospitalization
- Number of severe and moderate bleeding complications (GUSTO-definition, N Engl J Med. 1993;329:673–682) and the number of packed red blood cells transfused under VA-ECMO
- Infection probability: pulmonary, blood and VA-ECMO cannulaes

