11 DATA ANALYSIS AND STATISTICAL DETERMINATION

11.1 DESCRIPTION OF ANTICIPATED STATISTICAL ANALYSIS METHODS

11.1.1 Statistical analysis for the primary endpoint

The differences between the 2 study groups (i.e. intervention and controls) in the risk of all-cause mortality at day 30 following randomization will be studied using the Chi-2 test. To illustrate the association, both an odd-ratio and a hazard ratio will be provided. In addition, survival curves using the Kaplan-Meier method will be constructed.

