11.2 SAMPLE SIZE CONSIDERATION

We considered that mortality in cardiogenic patients supported with VA-ECMO will be 50% (based both on ELSO data, [name] data (*Crit Care Med.* 2008 May;36(5):1404-11) and study principal investigator's personal data (database of 150 patients)

The objective of the study is to demonstrate the superiority of the treatment with VA-ECMO plus moderate hypothermia as compared to VA-ECMO alone on mortality.

Therefore, considering a total event risk (for the primary endpoint) of 50 % in the control group, a sample size of N = 167 patients/group will detecting a 15% absolute difference in favor the VA-ECMO group using a chi-square test with a 80 % power and considering a two-sided global alpha level of 5% using the LanDe Mets method with O'BrienFleming boundary for one interim analysis (efficacy and futility) after inclusion of 2/3 of the patients.

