11.3 DEGREES OF STATISTICAL SIGNIFICANCE

A bilateral p value lower than 4.9% will be considered significant for the final analysis. A p value threshold lower than 5% is mandatory given the planned interim analyses to ensure a global alpha level at 5%.

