11.6 METHOD FOR ADDRESSING MISSING, INVALID OR UNUSED DATA

For the primary outcome, we do not expect missing variables. All-cause 30 days mortality is a straightforward outcome that does not require detailed information. Yet, in the unlikely case of missing vital status at 30 days, patients with missing data will be analyzed with the last observation being carried forward. In a sensitivity analysis, the worst case scenario method will be used (i.e. all patients with incomplete follow-up data died in the intervention group and died in the no intervention group).

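### The worst-case sensitivity analysis in section 11.6 counts missing patients as dead in both arms, so it is not a worst case for the superiority claim

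*Protocol*

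**What the plan says.** The primary endpoint is all-cause death by day 30 after randomization (section 3.3.1), and the objective is superiority of hypothermia (section 3.1). Section 11.1.1 states that "mortality at day 30 following randomization will be studied using the Chi-2 test", and section 11.8 includes every randomized patient.

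Section 11.6 expects no missing data for this endpoint. If vital status is nevertheless missing, the last observation is carried forward. One sensitivity analysis is named. It is called a worst-case method and is spelled out as "all patients with incomplete follow-up data died in the intervention group and died in the no intervention group". No other section defines it differently.

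**The concern.** A patient whose day-30 status is unknown was alive when last seen, so carrying the last observation forward counts that patient as a survivor in either arm. The sensitivity analysis moves the same patients to dead, again in either arm. Both analyses treat the two arms alike. A worst case for a superiority claim has to treat them in opposite ways, with missing patients dead under the experimental treatment and alive under control.

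What is at stake is a robustness statement. A report could say that the result survived a worst-case analysis when no such analysis was done. Some loss is possible: the trial is open, patients may be enrolled before consent and asked later to continue (section 13.2), and a patient who leaves may have objected to the use of the data (section 4.5.1).

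**Working it through.** **Inputs from the protocol.** 167 patients per group (sections 4.3.2 and 11.2); chi-square test (11.1.1); 50% control mortality, "considering a total event risk (for the primary endpoint) of 50 % in the control group"; a 15-point difference, "will detecting a 15% absolute difference"; 80% power (11.2); final threshold, "A bilateral p value lower than 4.9% will be considered significant for the final analysis".

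**Inputs assumed.** The death counts and the numbers missing. The protocol gives no missing rate, so cases from 2 to 10 missing in an arm are shown, balanced and unbalanced.

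**The plan's own figure.** n = [z(α/2)·√(2p̄(1−p̄)) + z(β)·√(p₁(1−p₁)+p₂(1−p₂))]² / (p₁−p₂)², with p₁=0.50, p₂=0.35, p̄=0.425. At two-sided 5% and 80% power this gives 169.3, so 170 per group. The stated 167 gives 79.5% power, which is close enough to accept 167 as the table size.

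**The three analyses as formulas.** Let d_H and d_C be known deaths and m_H and m_C the numbers missing, with 167 in each arm. The risk difference is control minus hypothermia.

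- Main analysis (missing = alive): RD = (d_C − d_H)/167
- Written rule (missing = dead in both arms): RD + (m_C − m_H)/167
- True worst case (dead in hypothermia, alive in control): RD − m_H/167

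The written rule is therefore more favourable than the true worst case by m_C/167. They agree only when no control patient is missing.

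**Test.** Uncorrected chi-square, z = RD / √(2p̄(1−p̄)/167), with p̄ the pooled proportion dead. For 64 v 83: p̄ = 147/334 = 0.440, RD = 19/167 = 0.114, standard error 0.0543, z = 2.094, p = 0.036. With 3 missing per arm:

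- Written rule: 67 v 86, RD still 19/167, z = 2.087, p = 0.037.
- True worst case: 67 v 83, RD = 16/167 = 0.096, z = 1.760, p = 0.078.

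Deaths and missing counts below are hypothermia v control.

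| Known deaths (main p) | Missing | Written rule: deaths, RD, p | True worst case: deaths, RD, p |
|---|---|---|---|
| 64 v 83 (0.036) | 2 v 2 | 66 v 85, 11.4, 0.037 | 66 v 83, 10.2, 0.061 |
| 64 v 83 (0.036) | 3 v 3 | 67 v 86, 11.4, 0.037 | 67 v 83, 9.6, 0.078 |
| 64 v 83 (0.036) | 2 v 0 | 66 v 83, 10.2, 0.061 | same |
| 62 v 84 (0.015) | 5 v 5 | 67 v 89, 13.2, 0.016 | 67 v 84, 10.2, 0.062 |
| 62 v 84 (0.015) | 2 v 5 | 64 v 89, 15.0, 0.006 | 64 v 84, 12.0, 0.028 |
| 62 v 84 (0.015) | 5 v 0 | 67 v 84, 10.2, 0.062 | same |
| 58 v 84 (0.004) | 8 v 8 | 66 v 92, 15.6, 0.004 | 66 v 84, 10.8, 0.048 |
| 58 v 84 (0.004) | 10 v 10 | 68 v 94, 15.6, 0.004 | 68 v 84, 9.6, 0.079 |

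The last pair of rows is the design effect: 0.50 × 167 = 83.5 and 0.35 × 167 = 58.5, taken as 84 and 58.

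Under balanced loss the risk difference is fixed, but p can drift because p̄ changes. With 80 to 88 control deaths and 1 to 17 missing per arm, no balanced case crossed 0.049. At much lower mortality a borderline result can: 43 v 60 deaths with 5 v 5 missing moves p from 0.044 to 0.0493.

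**The case against.** A reader might infer that the rule can never overturn a positive result. The figures do not support that. Because the main analysis counts missing patients as alive, counting them as dead works against hypothermia whenever that arm loses more patients. From 64 v 83, 2 v 0 missing moves p from 0.036 to 0.061, and when no control is missing the rule equals the true worst case. Differential loss therefore does not by itself make the rule empty; the direction of the imbalance decides.

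A reader might also infer that a few missing patients would undo the planned result. That holds for a borderline win such as 64 v 83. At the design effect, 8 missing per arm (4.8%) still leaves p below 0.049 under the true worst case.

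The protocol also gives reason to expect little loss. The endpoint is death at 30 days in intubated intensive-care patients, and section 4.1.9 provides for contact with the patient, the family or the primary care physician to establish vital status. The repeated verb in section 11.6 may be a slip for survival in the control arm. These points lower the severity. They do not make the rule fit its label, and an analyst who followed the text would run the wrong analysis.

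**Conclusion.** The point stands in this form: the analysis labelled worst case is not one. It leaves the risk difference unchanged when losses are equal, flatters hypothermia when controls lose more, and works against hypothermia only when the hypothermia arm loses more. Its shortfall against a true worst case is the number of missing controls divided by 167, about 0.6 points per missing control. In the assumed borderline case with 3 missing per arm, that is the difference between p=0.037 and p=0.078.

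The size depends on assumed death tables and missing counts, and on reading last observation carried forward as alive. The primary test, its threshold and the sample size are untouched. It should be fixed, but the documents do not support calling it a threat to the primary conclusion.

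**What to change.** Replace the definition in section 11.6 with: patients with unknown day-30 status are counted as dead in the hypothermia group and alive in the normothermia group. The mirror case (alive in hypothermia, dead in normothermia) may be added to give both bounds.

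The cost is one sentence, best settled before outcome data by arm are seen. The downside for the sponsor is that the sensitivity result can only be the same as, or less favourable than, the one from the written rule.

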11.7 MANAGEMENT OF AMENDMENTS TO THE ANALYSIS PLAN OF THE INITIAL STRATEGY

No amendments are expected. Amendments can be decided by the steering committee.

11.8 SELECTION OF SUBJECTS TO BE INCLUDED IN THE ANALYSIS

As per intention to treat analysis, every randomized patients will be included in the analysis.

12 CONTROL AND QUALITY ASSURANCE

12.1 ACCESS TO SOURCE DATA AND DOCUMENTS

The sponsor is responsible for obtaining the agreement of all parties involved in the study so as to guarantee direct access to all study sites, source data, source documents, and reports so that the sponsor may control data quality and perform an audit.

Investigators accept to give access to all relevant data and records to the sponsor (Sponsor's monitors, auditors, the Sponsor's Quality Assurance representatives) and all authorized Sponsor personnel, and regulatory authorities, under strict confidentiality condition and in compliance to the French regulatory.

12.2 STUDY MONITORING

Monitoring will be performed by the sponsor (Department of Research and Innovation CHRU de Nancy) during the study to ensure that compliance with the Protocol and applicable regulations is maintained, that data are collected in a timely, accurate and complete manner and that the investigator continues to have sufficient staff and facilities to conduct the study safely and effectively. Details of the monitoring visits will be work out in the sponsor monitoring plan.

13 ETHICAL CONSIDERATIONS AND REGULATIONS

13.1 REGULATORY AND ETHICAL CONSIDERATIONS

Before initiating a trial, according to the French local regulation, the sponsor (CHRU Nancy) should obtain approval/favorable opinion from the Institutional Review Board/Independent Ethics Committee (IRB/IEC) and authorization from the French Health Authorities for the reseach.

The sponsor and investigators commit that this research is conducted according to the protocol and his procedures, to the French local regulation (law n ° 2004-806 of August 9, 2004), as well as in agreement with Good Clinical Practices (I.C.H. version 4 of May 1, 1996 and Decision of November 24, 2006) and the Helsinki Declaration (Ethical Principles for Medical Research Involving Human Subjects, Tokyo 2004).

13.2 INFORMED CONSENT PROCESS

Before collecting the patient's consent, the investigator will give complete information about the proposed study.

In the particular context of this protocol, the persons include in this research may not be able to receive information about the study and give their consent before the implementation of the protocol due to their medical condition.

In this case, if a member of the patient's family (or support person defined in Article L.1111-6 - Appendix 5) is present, this person will be informed and consent will be gathered.

In the absence of a family member or support person, the investigator will include the patient in the study and will gather the consent of the family member or support person as soon as possible.

The patient will be asked to give his/her consent for the continuation of the trial when his/her condition will allow.

Patient, family member or support person, is free to refuse participation in the study and may at any time and for whatever reason withdraw its consent.

The consent form will be signed in two originals copy by the subject and the investigator and a member of the family / support person if applicable:

- An exemplary will be given to the subject or family member / support person if applicable

- An exemplary will be retained and archived by the investigator

Particular case:

Given the studied pathology (cardiogenic choc), the prognosis for survival of the patient included in emergency setting is threatened and the death probability stays high.

If the patient died after inclusion in emergency setting and no support person is written in the medical file or support person can't be contacted by investigator, consent must be gathered from a family

member. If the patient does not have a family or if the investigator can't contact the family or if the investigator can't contact again family after obtaining an oral agreement from a family member, the investigator will have to write all the steps taken in the medical file and note his inability to contact the family.

The inclusion of the patient in the protocol and the use of the data are possible without signed consent if all these 3 conditions are met:

- The patient died after inclusion in emergency setting without family or support person, properly documented in the medical file by the investigator.

- no support person is noted in the medical file or the inability to contact support person or to contact again support person after obtaining an oral agreement in spite of the implemented efforts properly documented by investigator in the medical file.

- the inability to contact family member or to contact again family member after obtaining an oral agreement in spite of the implemented efforts properly documented by investigator in the medical file.

.

13.3 PROTOCOL AMENDMENT

Any change or addition to the protocol can only be made in a written protocol amendment (modification of an inclusion criterion, extending the inclusion period, participation of new centers ...) that must be approved by the sponsor, French Health Authorities and the IRB/IEC prior to implementation.

13.4 PATIENT DATA CONFIDENTIALITY

Throughout the study, confidentiality shall be observed, at all times, by all parties involved, and all data shall be secured against unauthorized access.

Confidentiality of each subject shall be preserved in reports and any publication of the results.

Only authorized Sponsor staff and regulatory authorities may have access to these confidential files.

The data collected during the study will be performed according to the French local regulation (Commission Nationale de l'Informatique et des Libertés (CNIL), in compliance with the MR001 methodology)

13.5 ARCHIVING STUDY DOCUMENTS AND STUDY DATA

All study documents including patient's identification list and signed informed consent should be keep for at least 15 years. For each patient, documentation must clearly specify the following:

- Participation of the patient in the study (patient and study's identification),
- Concomitant treatments or medications,
- Any visit to the hospital, particularly those visits made for the sole purposes of the study,
- Serious adverse events (SAEs).

13.6 AUDIT AND INSPECTION

Audits or inspections may be performed at any time by persons mandated by the sponsor and independent of those in charge of the study or by French Health Authority respectively.

Investigators accept to give access to all relevant data and records to the auditors and inspector. If an inspection of the clinical site is requested by the French Health Authority, the investigator must inform the sponsor immediately that this request has been made.

14 INSURANCE

14.1 INSURANCE

The sponsor has subscribed an insurance for the duration of the study guaranteeing its own civil liability as well as that of any stakeholder involved in the conducting of the study, regardless of the nature of existing ties between the stakeholders and the sponsor.

15 PUBLICATION POLICY

15.1 FINAL RESEARCH REPORT

The final report of the research will be written collaboratively by the coordinator and the biostatistician mandated for this search. This report will be submitted to each of the investigators for review. Once a consensus has been reached, the final version must be endorsed with the signature of each of the investigators and sent to the sponsor as early as possible after the effective end of the research.

Data is the property of the sponsor. The conditions for data transfer of all or part of the study database are decided by the study sponsor.

"CHRU Nancy" should be mentioned as sponsor of this study.

The publications resulting from this work will be labeled by « The study was supported by a grant from the French Ministry of Health (Programme de Recherche Hospitalier National 2015) »

16 APPENDIX

Appendix A: Common management for all included patients treated with VA-ECMO before and during study intervention

1. ECMO initiation;

Veno-Arterial ECMO (VA-ECMO) support will be used. The extracorporeal system will consist of polyvinyl chloride tubing, a membrane oxygenator, a centrifugal pump, and percutaneous arterial and venous femoral cannulae. An oxygen/air blender will be used to ventilate the membrane oxygenator. An 7-10-Fr cannula will be inserted distally into the superficial femoral artery to prevent severe leg ischemia. Heparin boluses at the time of VA-ECMO implantation will be discouraged however a low dose bolus is permitted according to the experience of the ECMO team.

2. Initial parameter settings for VA-ECMO

The pump flow will be set to 3.5-5 l/min, to provide adequate systemic perfusion. Pump flow might be reduced in case of cessation of LV ejection or major pulmonary edema. Percentage of oxygen contained in the ventilating gaseous air–oxygen mixture will be adjusted to obtain PaO2 between 65 and 90 mmHg and/or arterial oxygen saturation >90%. The membrane ventilation will be adjusted to maintain PaCO2 between 40 and 45 mmHg.

3. VA-ECMO monitoring (extracorporeal circuit, anticoagulation, possible complications)

The VA-ECMO circuit will be monitored several times daily by the medical and nursing team caring for the patient and at least once every 48 hours by a perfusionist. Circuit and cannula surveillance is intended to verify the correct functioning of the device and early screening for complications (leg ischemia, fibrin deposits or clots on the VA-ECMO membrane, clots in the cannulae or in the pump, bleeding or signs of inflammation or cutaneous infection at the cannula insertion sites, unexpected drop of the VA-ECMO outflow, appearance of clinical or biological signs of intravascular hemolysis). Should any of these complications occur, a medical–surgical consultation will be held to discuss the best therapeutic approach to take.

Anticoagulation will be obtained with non-fractionated heparin to a target aPTT of 55-70 sec or heparinemia (antiXa activity) between 0.2 and 0.3 IU/ml. A bolus of heparin is not encouraged at the time of circuit implantation. Should severe bleeding occur that is not immediately controllable by specific treatment, heparin will be discontinued.

Intravascular hemolysis will be sought should unexpected dark urine be excreted or in the case of obvious circuit dysfunction. It is recommended that plasma free hemoglobin be measured every 48 hours and immediately if hemolysis linked to the circuit is suspected.

The membrane and VA-ECMO circuit will be changed in the following situations: massive intravascular hemolysis linked to the device, severe thrombopenia linked to the circuit, clots preventing the pump and/or lines from functioning properly or systemic defibrination.

The hemoglobin threshold for red cells transfusion will be 9-10 g/dl (may be decreased to 7-8 g/dl if the patient is stabilized and does not have residual myocardial ischemia). Platelet transfusion will be discouraged except when severe thrombopenia is associated by bleeding complications or when platelet count will be <20 G/L.

Connecting an extrarenal dialysis circuit to the VA-ECMO circuit will be permitted under strict supervision of perfusionnists.

4. Intra-aortic balloon pump (IABP) support in addition to VA-ECMO

An IABP will be inserted according to the physician choice in the contralateral femoral artery. A strategy of liberal use of IABP has been associated with less pulmonary edema and better LV unloading in patients with severe LV dysfunction under VA-ECMO.

5. Weaning criteria and ECMO weaning

Weaning from VA-ECMO should not be attempted in the first 48 hours. Before a first weaning trial, the patient should be hemodynamically stable, with baseline mean arterial pressure (MAP) > 60 mmHg in the absence or at low doses of vasoactive agents and pulsatile arterial waveform maintained for at least 24 hours. The weaning will be conducted under echocardiographic monitoring. The ECMO flow will be decreased progressively to a minimum of 1–1.5 L/min. If mean blood pressure is constantly > 60 mmHg during the trial, the VA-ECMO flow rate will be returned to its baseline value. VA-ECMO removal will be considered if the patient does not have end-stage cardiac disease, tolerates the full weaning, and has LVEF \geq 20–25%, aortic velocity-time integral \geq 12 cm and lateral mitral annulus peak systolic velocity of \geq 6 cm/s under minimal VA-ECMO support.

Appendix B : ECMO device

Centres	Туре	Nom du dispositif (dénomination commune et commerciale)	Marque	Fournisseur	N° Marquage CE
	Echangeur thermique	HU 35	Maquet	Maquet	CE 0124
	Pompe	Rotaflow Cardiohelp	Maquet Maquet	Maquet Maquet	CE 0124 CE 0124
Nancy	Oxygénateur	BE-PLS 2051 BE-PLS 2050	Maquet	Maquet	CE 0124
	Membrane (polymethylpentene)	Quadrox	Maquet	Maquet	
	Echangeur thermique	Biocal 370 Deltastream HC IPX1	Medtronic Medos Stockert	Medtronic Xenios Sorin	CE 0123 CE 0123 CE 0123
Nantes	Pompe	Deltastream DP3 Rotaflow Biomedicus	Medos Maquet IBC	Xenios Maquet Xenios	CE 0123 CE 0124 CE 0481
	Oxygénateur	Hilite	Medos	Xenios	CE 0481
	Membrane	Membrane Hilite	Medos	Xenios	
	Echangeur thermique	HU 35	Maquet	Maquet	CE 0124
Bordeaux	Pompe	Rotaflow	Maquet	Maquet	CE 0124
bordeaux	Oxygénateur	Quadrox ID Adult	Maquet	Maquet	CE 0124
	Membrane	Quadrox	Maquet	Maquet	
	Echangeur thermique	Réchauffeur	Maquet	Maquet	CE 0124
Daria (Dichat)	Pompe	Rotaflow coude	Maquet	Maquet	CE 0413
Paris (Bichat)	Oxygénateur	Sechrisy	Maquet	Maquet	CE 0124
	Membrane	Quadrox	Maquet	Maquet	
	Echangeur thermique	Stockert (3T) HU35	Stockert Maquet	Sorin Maquet	CE 0123 CE 0124
Toulouse	Pompe	Rotaflow Cardiohelp D 905	Maquet Maquet Sorin	Maquet Maquet Sorin	CE 0124 CE 0124 CE 0123
	Oxygénateur	Quadrox	Maquet	Maquet	CE 0124
	Membrane	Quadrox	Maquet	Maquet	
	Echangeur thermique	HU 35 70103.3557	Maquet	Maquet	CE 0124
Genoble	Pompe	ROTAFLOW CONSOLE 706045	Maquet	Maquet	CE 0124

	Oxygénateur	Quadrox BE-HQV 50600	Maquet	Maquet	CE 0124
	Membrane	Quadrox	Maquet	Maquet	
	Echangeur thermique	HU 35	Maquet	Maquet	CE 0124
Clermont-Ferrand	Pompe	Rotaflow	Maquet	Maquet	CE 0124
Clermont-Ferrand	Oxygénateur	Quadrox	Maquet	Maquet	CE 0124
	Membrane	Quadrox	Maquet	Maquet	
	Echangeur thermique	HU 35	Maquet	Maquet	CE 0124
Marseille	Pompe	Cardiohelp Biomedicus	Maquet Medtronic	Maquet Medtronic	CE 0124 CE 0123
	Oxygénateur	Quadrox PLS oxygenator HLS Module Advance 7.0	Maquet	Maquet	CE 0123
	Membrane	Quadrox	Maquet	Maquet	
	Echangeur thermique	Générateur thermique 3 T	Stockert	Sorin	CE 0123
Rouen	Pompe	ROTAFLOW	Maquet	Maquet	CE 0413
	Oxygénateur	Quadrox ID Adult	Maquet	Maquet	CE 0124
	Membrane	Quadrox	Maquet	Maquet	
	Echangeur thermique	Générateur thermique	Stochert	Sorin	CE 0123
Strasbourg	Pompe	Révolution Biomédicus Rotaflow	Sorin Medtronic Maquet	Sorin Medtronic Maquet	CE 0123 CE 0123 CE 0123
	Oxygénateur	Oxygénateur	Euroset	Euroset	CE 0123
	Membrane	Membrane	Euroset	Euroset	
	Echangeur thermique	Heater Unit 35	Maquet	Maquet	CE 0124
	Pompe	Rotaflow Cardiohelp Base Unit	Maquet Maquet	Maquet Maquet	CE 0124 CE 0124
Amiens	Oxygénateur	Quadrox PLS oxygenator HLS Module Advance 7.0	Maquet	Maquet	CE 0124
	Membrane	Quadrox	Maquet	Maquet	
	Echangeur thermique	HU 35	Maquet	Maquet	CE 0123
	Pompe	Revolution	Sorin	Sorin	CE 0123
Montptellier	Oxygénateur	Alone (adulte) EOS	Euroset Sorin	Euroset Sorin	CE 0123 CE 0123 CE 0123
	Membrane	Membrane	Euroset	Euroset	
Paris (La Pitié)	Echangeur thermique	HU 35	Maquet	Maquet	CE 0124

	Pompe	Cardiohelp Rotaflow Evolution	Maquet Maquet Sorin	Maquet Maquet Sorin	CE 0124 CE 0124 CE 0123
	Oxygénateur	HLS Module Advance 7.0 Quadrox EOS	Maquet Maquet Sorin	Maquet Maquet Sorin	CE 0124 CE 0124 CE 0124
	Membrane	Quadrox Membrane EOS	Maquet Sorin	Maquet Sorin	
Besançon	Echangeur thermique	HU 35	Maquet	Maquet	CE 0124
	Pompe	STOCKERT	Sorin	Levinova	CE 0123
	Oxygénateur	EOS	Sorin	Levinova	CE 0123
	Membrane	D905	D 905	Levinova	
Rennes	Echangeur thermique	Deltastream	Medos	Xenios	CE 0123
	Pompe	Deltastream MDC	Medos	Xénios	CE 0123
	Oxygénateur	300000072 MEH2C3943	Medos	Xenios	CE 0481
	Membrane	Medos	Medos	Xenios	
Lyon	Echangeur thermique	HU 35 Deltastream HC	Maquet Medos	Maquet Xenios	CE 0124 CE 0123
	Pompe	Rotaflow Deltastream MDC	Maquet Medos	Maquet Xenios	CE 0413 CE 0123
	Oxygénateur	Quadrox Hilite	Maquet Medos	Maquet Medos	CE 0124 CE 0481
	Membrane	Quadrox Membrane Hilite	Maquet Medos	Maquet Medos	
Annecy	Echangeur thermique	Heater-Cooler	Stockert S III	Sorin	CE 0123
	Pompe	Stockert scpc	Sorin	Sorin	CE 0120
	Oxygénateur	Sorin	Sorin	Sorin	CE 0123
	Membrane	Membrane Sorin	Sorin	Sorin
